## 12.0 CRITERIA FOR THERAPEUTIC RESPONSE/OUTCOME ASSESSMENT

This is a pilot study which aims to obtain pharmacokinetic data on the biodistribution of FMISO in patients with colorectal cancer. It will also assess the feasibility of detecting hypoxia by non-invasive F-FMISO PET imaging in colorectal carcinoma patients, and to do this will utilize a dynamic PET acquisition sequence that will provide kinetic tumor uptake data, which when combined with blood clearance kinetics through compartmental modeling may provide useful parametric maps of the variation of intra-tumor hypoxia. Whereas, in this study, we will not obtain direct gold-standard measurements of tumor hypoxia using a pO2 microelectrode, we and others have confirmed by autoradiography that the F-FMISO tracer distribution accurately correlates with both exogenous (pimonidazole) and endogenous (HIF-1α and carboanhydrase 9) immunohisto-chemical markers of hypoxia.

## 13.0 CRITERIA FOR REMOVAL FROM STUDY

If at any time the patient withdraws consent he/she will be removed from the study.

If at any time the patient develops unacceptable toxicity he/she will be removed from the study. Although we have never had any adverse effects from the FMISO administration and none have been reported elsewhere (see section 11.0), allergic reaction is always a possibility and any patient experiencing this would be sent immediately to the Urgent Care unit for treatment, reported to the Principal Investigator, and removed from the study.

If at any time the patient is found to be ineligible for the protocol as designated in the section on Criteria for Patient/Subject Eligibility (i.e., a change in diagnosis), the patient will be removed from the study.

Please note that all patients whether included in this study or not will receive the standard of care radiation treatments.

## 14.0 BIOSTATISTICS

This is a feasibility study of using F-FMISO PET to detect tumor hypoxia in colorectal cancer. Prospective patients will be scanned using F-FMISO PET to identify the hypoxic regions. Analysis of the PET data will be conducted by one

of the physicists in Nuclear Medicine, who will use a software package designed to analyze on a voxel by voxel basis the kinetics of FMISO uptake and clearance in the tumors.

The primary objective of the study is to determine the feasibility of the imaging with F-FMISO in colorectal cancer patients. Feasibility is defined as identifying regions of interest (ROI) in the F-FMISO PET scan. In an earlier protocol with FMISO in head and neck cancer, 18 of 20 patients had identifiable ROIs. Since published data (26, 27) reveal that upwards of 40% of all, non selected early and advanced rectal cancers are considered to be hypoxic, and since the patients we will be studying in this protocol have large bulky, locally advanced rectal cancers, we anticipate that perhaps as many as 70% of our rectal cancers will be hypoxic. Because of differences in histology between head and neck cancers (squamous carcinoma) and rectal cancers (adenocarcinoma) and possible differences in excretion, we consider identifying ROIs in 50% of patients to be desirable and 30% to be too low.

Two criteria will be used for identifying hypoxia voxels. The first approach is the traditional method reported in the literature by the University of Washington group which defines hypoxia as tumor voxels for which the concentration ratio of FMISO between tumor to blood FMISO is 1.2 or greater, at a single late imaging time point. The second approach utilizes the kinetic profile of FMISO uptake and clearance from each tumor voxel. With this approach, hypoxic voxels are defined as those for which the uptake is slow and continuously rising vis-a-vis highly perfused regions where the initial uptake is high but continuously declining. One reason for employing the second approach is that there is evidence that a single late imaging time point can be ambiguous and not uniquely define the tumor hypoxic regions without knowledge of the history of the signal intensity to that voxel.

As just mentioned, using both F-FMISO radioactivity concentration and kinetic uptake profile data in the tumor to signify a positive scan, we propose to evaluate the feasibility using a 2-stage design. In the first stage, 15 patients will receive an F-FMISO PET scan. If 4 or fewer patients have identifiable ROIs, then the study will be stopped. If 5 or more have ROIs then an additional 15 patients at most will be scanned. F-FMISO imaging will be considered successful if ROIs are present in 13 or more of the 30 patients. However, even if the first 13 of 15 patients scanned have identifiable ROIs, we will continue to scan up to 15 additional patients in order to obtain a spectrum of hypoxic fraction versus treatment response. Pre-clinical studies are underway to determine the correspondence between the ROIs in the scan and hypoxia.

In addition to visualizing these regions we want to determine their volume as a proportion of the entire tumor volume. If the ROIs correspond to hypoxia then the larger these proportions, the more hypoxic the tumor and potentially worse the prognosis. This data will provide preliminary information that could be used for a

future trial with the F-FMISO imaging as a prognostic marker. If the imaging is successful, at least 13 patients will provide information for this objective which will be valuable preliminary data.

Distribution of F-FMISO based on the pharmacokinetic data will be assessed using descriptive statistics (mean, standard deviation, etc.) and graphic tools. For instance, we will use both histograms and box plots to depict the data.

The microdistribution of F-FMISO will be analyzed quantitatively through digital autoradiography.

This design has 8% type I error and 80.4% power.

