## 2.0 OBJECTIVE AND SCIENTIFIC AIMS

Our primary objective is to determine the feasibility of a non-invasive method of detecting hypoxia, using F-FMISO-PET imaging in colorectal cancer patients. Feasibility is defined as the ability to identify regions of interest (ROI) on the F-FMISO-PET images that distinguish between hypoxic and normoxic regions within colorectal tumors.

Secondary objectives include determining the volume of hypoxic tumor ROIs as a proportion of the entire tumor volume by this non-invasive imaging technique. ROIs are defined as those voxels, within the tumor volume defined on FDG PET/CT, for which the F-FMISO radioactivity concentration is greater than 1.2 times that

measured in blood. Selection of this threshold is based on the largest body of F-FMISO studies in humans (20, 21).

We will also obtain pharmacokinetic data on the biodistribution of F-FMISO in patients with colorectal cancer to determine the optimal interval between drug administration and PET imaging.

Digital autoradiography, when performed, will allow us to determine the correspondence between the micro-distribution of F-FMISO and the tumor histology.

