## 4.0 OVERVIEW OF STUDY DESIGN AND INTERVENTION

## 4.1 Design

All patients will undergo the standard of care for their colorectal cancer and will have an FDG PET/CT scan performed within six weeks of a dynamic F-FMISO PET/CT scan. We will accept FDG PET scans not performed at MSKCC if the outside study was performed as a dedicated PET/CT and the full data set (including all CT and PET images) is submitted digitally to us accompanied by a report clearly indicating the administered activity, uptake time and blood glucose level at the time of the study. The patient will receive no treatment between the two scans. Both scans will be performed before radiochemotherapy. The FDG PET scan will be used to delineate the tumor volume. The accompanying CT of both FDG and F-FMISO will be co-registered, to allow selection of the F-FMISO intra-tumoral hypoxic voxels.

Regions of interest (ROI) corresponding to hypoxic tumor sub-volumes will be defined as those voxels, within the tumor volume defined on FDG PET/CT, for which the F-FMISO radioactivity concentration is greater than 1.2 times that measured in blood. The selection of this threshold is in concordance with the largest body of F-FMISO studies in man (20, 21), which were successfully adopted in our own studies in head and neck cancers by [name].

This is a feasibility trial using a 2-stage design. In the first stage, 15 patients will receive an F-FMISO PET scan. If 4 or fewer patients have ROIs, the study will be stopped but if 5 or more patients have ROIs then an additional 15 patients at most will be scanned. We will therefore scan a maximum of 30 patients in order

to determine the hypoxia fraction in colorectal cancer using F-FMISO. We anticipate the need to enroll approximately 50 patients to account for withdrawals of consent or inability of subjects to complete protocol requirement in order to achieve our target of 30 completed scans. Once this has been established, we propose a larger trial in order to correlate hypoxia fraction with treatment outcome.

Digital autoradiography will be performed on frozen tumor tissue sections obtained from the resected specimen in patients who undergo surgery on the same day as the F-FMISO PET in order to determine the micro-distribution of F-FMISO (see details in Section 4.2, "Intervention").

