## 10.0 EVALUATION DURING TREATMENT/INTERVENTION

There are no follow-up requirements for this study. All patients will undergo standard of care for their colorectal cancer and will be evaluated accordingly.

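### Does Section 14.0 promise a treatment-response comparison that the study cannot deliver, and does it limit the hypoxic fraction to ROI-positive patients?

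*Combined protocol and SAP*

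**What the plan says.** **Reason for continuing.** Section 14.0 stops the study if 4 or fewer of the first 15 patients have ROIs and otherwise scans at most 15 more. For the case where 13 of the first 15 are already positive, it adds that "we will continue to scan up to 15 additional patients in order to obtain a spectrum of hypoxic fraction versus treatment response". Section 4.1 gives the purpose of the maximum of 30 scans as "to determine the hypoxia fraction in colorectal cancer using" the tracer, and continues: "Once this has been established, we propose a larger trial in order to correlate hypoxia fraction with treatment outcome". Section 10.0 states: "There are no follow-up requirements for this study". Section 2.0 lists no response objective. Section 12.0 carries therapeutic response in its title but defines no response measure.

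**Patients counted.** Section 14.0 says that "imaging will be considered successful if ROIs are present in 13 or more of the 30 patients". It then turns to ROI volume as a proportion of tumor volume and says that, if imaging succeeds, "at least 13 patients will provide information for this objective which will be valuable preliminary data". Of the same proportions it says "This data will provide preliminary information that could be used for a" later trial of the imaging as a prognostic marker. Section 2.0 sets the voxel rule: "ROIs are defined as those voxels, within the tumor volume defined on FDG PET/CT, for which the" tracer concentration exceeds 1.2 times that in blood.

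**The concern.** There are two grounds for worry.

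First, Section 14.0 seems to justify up to 15 further research scans by a comparison that the study is not set up to make. A reader of that section would expect a response analysis; a reader of Section 4.1 would not. Response would also lack a single meaning here. Eligibility covers any colorectal adenocarcinoma, and some patients have surgery on the day of the scan. If the scans had no other purpose, patients would be exposed for a result that could not be produced.

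Second, the figure of at least 13 could be read as the analysis set for the hypoxic fraction. A mean among ROI-positive patients and a mean among all scanned patients answer different questions. Planners of the later prognostic trial could mistake the first for the second and expect more hypoxia than an unselected group has.

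**Working it through.** **1. The plan's own figures.** Inputs from Section 14.0: 15 patients in stage 1, stop at 4 or fewer positive, 15 more in stage 2, success at 13 or more of 30, ROI rate 30% too low and 50% desirable. With X and Y independent Binomial(15, p),

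P(success | p) = sum over x = 5 to 15 of P(X = x) × P(Y ≥ max(0, 13 − x)).

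| p | P(stop at stage 1) | P(success) | Stated |
|---|---|---|---|
| 0.30 | 0.515 | 0.0805 | 8% |
| 0.50 | 0.059 | 0.8043 | 80.4% |

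Both stated figures reproduce. When x is 13 or more, the second factor is 1. So neither the decision to scan on after 13 positives nor the reason given for it alters the type I error or power.

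**2. How often the clause applies.**
- At p = 0.50, P(X ≥ 13) = (105 + 15 + 1)/32768 = 0.0037.
- At the hoped-for 70%, P(X ≥ 13) = 105 × 0.7^13 × 0.3^2 + 15 × 0.7^14 × 0.3 + 0.7^15 = 0.127.
- Stage 2 opens with probability 1 − 0.059 = 0.941 at p = 0.50. Unless 13 positives have already been seen, its scans are needed for the primary decision.

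**3. Grounds for the scans without the phrase.** Section 4.1 wants up to 30 scans for the hypoxia fraction. Section 2.0 makes that fraction a secondary objective. Both grounds hold even when 13 of 15 are positive. Removing the words about response would leave every scan, decision and listed objective as it is.

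**4. The count of 13.** Success requires at least 13 ROI-positive patients, so at least 13 patients have a region whose volume can be measured. The sentence is correct as a lower bound. At the minimum, 13 positives leave 30 − 13 = 17 negatives, and no passage removes them.

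Let k be the number of positives among 30, and m₊ and m₋ the mean fractions in positives and negatives. Then

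positives-only mean / all-patient mean = 30 m₊ / (k m₊ + (30 − k) m₋).

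If m₋ = 0 this equals 30/k. Over successful trials:

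| p | Mean positives | Mean negatives | Mean of 30/k |
|---|---|---|---|
| 0.50 | 15.93 | 14.07 | 1.92 |
| 0.70 | 21.01 | 8.99 | 1.45 |

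The ratio falls toward 1 as m₋ approaches m₊, so 1.92 and 1.45 are ceilings as long as negatives have, on average, no larger a fraction than positives. The documents do not support m₋ = 0. Section 14.0 calls a scan positive using concentration and kinetic profile together, whereas Section 2.0 defines the fraction by the blood ratio alone. If both criteria must be met, a negative scan can still contain voxels above 1.2 times blood. The ratios therefore show how far apart two readings could lie; they do not estimate a bias in a planned analysis.

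**The case for a change.** The strongest case for acting is that response is the only reason Section 14.0 itself gives for scanning on after 13 of 15 positives, and the study has no means of delivering it. Two sentences would put both points right at no cost to patients, and the data are meant to feed a later trial.

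The inconsistency is real. No response variable, timing or analysis exists, and the documents do not explicitly plan to collect response from routine records. That part of the objection stands as a remark on wording.

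It carries less weight as a criticism of the design. A spectrum is descriptive language in a feasibility study, and an informal look followed by a larger correlational trial is a coherent sequence. Section 10.0 goes on to say that patients are evaluated under their standard care, so a description from charts is not excluded. On the second point, the objection needs an intention to discard negatives that no passage states. The proposed rewording would also fix the ratio-only definition for the fraction while leaving the kinetic criterion unaddressed, which goes beyond a clarification.

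**Conclusion.** No change to the plan follows. The reference to treatment response is a clerical inconsistency with Section 4.1. It affects no scan, stopping rule, error rate or planned analysis, and it concerns a situation with probability 0.4% at a true ROI rate of 50% and 13% at 70%. Anyone running the study would follow Section 4.1 and make no formal response comparison, or would give at most an exploratory description from routine records.

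The count of at least 13 is a correct minimum. An analyst would report the fraction in all scanned patients with an evaluable tumor volume and label any positives-only summary as such, which the plan already permits. The possible difference between the two summaries, at most about 1.92-fold at 50% and 1.45-fold at 70% on average over successful trials, depends on an assumption of zero fraction in every negative scan that the documents do not support.

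The probabilities assume independent patients with a common ROI rate; those conditional on success also assume that all 30 scans are completed.

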## 15.0 SUBJECT REGISTRATION AND RANDOMIZATION PROCEDURES

# 15.1 Research Participant Registration

Confirm eligibility as defined in the section entitled Inclusion/Exclusion Criteria. Obtain informed consent, by following procedures defined in section entitled Informed Consent Procedures. During the registration process registering individuals will be required to complete a protocol specific Eligibility Checklist. The individual signing the Eligibility Checklist is confirming that the participant is eligible to enroll in the study. Study staff are responsible for ensuring that all institutional requirements necessary to enroll a participant to the study have been completed. See related Clinical Research Policy and Procedure #401 (Protocol Participant Registration).

## 16.0 DATA MANAGEMENT ISSUES

A Research Study Assistant (RSA) will be assigned to the study. The responsibilities of the RSA include project compliance, data collection, abstraction and entry, data reporting, regulatory monitoring, problem resolution and prioritization, and coordinate the activities of the protocol study team.

The data collected for this study will be entered into a secure database. Source documentation will be available to support the computerized patient record. All research material from this study will be handled with the same confidentiality as patient's other medical data.

## 16.1 Quality Assurance

Weekly registration reports will be generated to monitor patient accruals and completeness of registration data. Routine data quality reports will be generated to assess missing data and inconsistencies. Accrual rates and extent and accuracy of evaluations and follow-up will be monitored periodically throughout the study

period and potential problems will be brought to the attention of the study team for discussion and action

Random-sample data quality and protocol compliance audits will be conducted by the study team, at a minimum of two times per year, more frequently if indicated.

# 16.2 Data and Safety Monitoring

The Data and Safety Monitoring (DSM) Plans at Memorial Sloan-Kettering Cancer Center were approved by the National Cancer Institute in September 2001. The plans address the new policies set forth by the NCI in the document entitled "Policy of the National Cancer Institute for Data and Safety Monitoring of Clinical Trials" which can be found at:

http://cancertrials.nci.nih.gov/researchers/dsm/index.html. The DSM Plans at MSKCC were established and are monitored by the Clinical Research Administration. The MSKCC Data and Safety Monitoring Plans can be found on the MSKCC Intranet at: http://mskweb2.mskcc.org/irb/index.htm

There are several different mechanisms by which clinical trials are monitored for data, safety and quality. There are institutional processes in place for quality assurance (e.g., protocol monitoring, compliance and data verification audits, therapeutic response, and staff education on clinical research QA) and departmental procedures for quality control, plus there are two institutional committees that are responsible for monitoring the activities of our clinical trials programs. The committees: *Data and Safety Monitoring Committee (DSMC)* for Phase I and II clinical trials, and the *Data and Safety Monitoring Board (DSMB)* for Phase III clinical trials, report to the Center's Research Council and Institutional Review Board.

During the protocol development and review process, each protocol will be assessed for its level of risk and degree of monitoring required. Every type of protocol (e.g., NIH sponsored, in-house sponsored, industrial sponsored, NCI cooperative group, etc.) Will be addressed and the monitoring procedures will be established at the time of protocol activation

## 17.0 PROTECTION OF HUMAN SUBJECTS

Risks of Study Participation: Potential risks as outlined in section 11.0 (Toxicities and Side Effects) will be discussed with patients as part of the informed consent process, and patients will be watched closely for signs of adverse events. Whether or not a patient decides to participate in this study, he or she will receive the current standard of care for their specific disease site.

Financial Costs to Patients: All diagnostic and therapeutic interventions except for the F-FMISO-PET scans, research blood draws, and digital

autoradiography, are part of the current routine care of patients eligible for this study. A research grant will cover the cost of the F-FMISO-PET scans, research blood draws, and digital autoradiography. There are no additional financial costs to the patient beyond the charges routinely incurred as part of standard medical care.

Patient Confidentiality: Patient/subject privacy and confidentiality will be maintained according to MSKCC guidelines and all data derived from this study will be kept in a secure database. All data and results will be anonymously reported with regard to individual subjects.

Voluntary nature of the study: Subjects will be made aware of the voluntary nature of the study as part of the informed consent process. They will be allowed to withdraw participation at any time without the risk of alteration in the quality of their medical care.

# 17.1 Privacy

MSKCC's Privacy Office may allow the use and disclosure of protected health information pursuant to a completed and signed Research Authorization form. The use and disclosure of protected health information will be limited to the individuals described in the Research Authorization form. A Research Authorization form must be completed by the Principal Investigator and approved by the IRB and Privacy Board.

## 17.2 Serious Adverse Event (SAE) Reporting

An adverse event is considered serious if it results in ANY of the following outcomes:

- Death
- A life-threatening adverse event
- An adverse event that results in inpatient hospitalization or prolongation of existing hospitalization
- A persistent or significant incapacity or substantial disruption of the ability to conduct normal life functions
- A congenital anomaly/birth defect
- Important Medical Events (IME) that may not result in death, be life threatening, or require hospitalization may be considered serious when, based upon medical judgment, they may jeopardize the patient or subject and may require medical or surgical intervention to prevent one of the outcomes listed in this definition

Note: Hospital admission for a planned procedure/disease treatment is not considered an SAE.

SAE reporting is required as soon as the participant signs consent. SAE reporting is required for 30-days after the participant's last investigational treatment or intervention. Any events that occur after the 30-day period and that are at least possibly related to protocol treatment must be reported.

If an SAE requires submission to the IRB office per IRB SOP RR-408 'Reporting of Serious Adverse Events', the SAE report must be sent to the IRB within 5 calendar days of the event. The IRB requires a Clinical Research Database (CRDB) SAE report be submitted electronically to the SAE Office as follows: For IND/IDE trials: Reports that include a Grade 5 SAE should be sent to [contact]. All other reports should be sent to [contact].

For all other trials: Reports that include a Grade 5 SAE should be sent to [contact]. All other reports should be sent to [contact].

The report should contain the following information:

Fields populated from CRDB:

- Subject's initials
- Medical record number
- Disease/histology (if applicable)
- Protocol number and title

Data needing to be entered:

- The date the adverse event occurred
- The adverse event
- The grade of the event
- Relationship of the adverse event to the treatment (drug, device, or intervention)
- If the AE was expected
- The severity of the AE
- The intervention
- Detailed text that includes the following
  - o A explanation of how the AE was handled
  - o A description of the subject's condition
  - o Indication if the subject remains on the study
- If an amendment will need to be made to the protocol and/or consent form
- If the SAE is an Unanticipated Problem

The PI's signature and the date it was signed are required on the completed report.

For IND/IDE protocols:

The CRDB SAE report should be completed as per above instructions. If appropriate, the report will be forwarded to the FDA by the SAE staff through the IND Office.

17.2.1

Any additional SAE reporting information required by the sponsor or drug supplier should be included in this section.

